#### 10.9 Destruction, return, and recall devices

All units are to be returned to Afferent Medical Solutions upon trial completion. Afferent will arrange for the disposal of all the units in an appropriate and controlled manner, upon the request from the Chief Investigator following accountability checks by the allocated monitor. The Sponsor should return the units to Afferent Medical Solutions Ltd, [name], UK. Separate earclips will be used to train participants and are to be disposed of by the Research Nurse in accordance with the clinical unit's standard operating procedures.

Regulations require that disposal of electrical equipment, including used and unused medical devices, is handled in a controlled manner. Devices that may be contaminated after use or that may contain chemicals or elements that may be hazardous to people or the environment will be disposed of in accordance with the applicable government regulations. Afferent will be responsible for the disposal of all devices and will ensure their disposal complies with Restrictions of Hazardous Substances (RoHS) and in accordance with the applicable government regulations. In case of a device recall, Afferent will be responsible for coordinating with the investigator and managing the process in a controlled manner.

# 10.10 Usage schedules

- First administration will be for duration of mechanical thrombectomy [which typically lasts two hours]
- Second administration will be the morning after the mechanical thrombectomy [0800-1200h] which typically lasts one hour.
- No changes to usage schedule are required for different age groups or demographics.

#### 10.11 Usage modifications and delays

• It is not envisaged that any modification in device usage or device itself during the conduct of the trial, except if a person develops local irritation/dermatitis which makes it difficult to use the clips to the ear. In that case, we will withhold treatment until the person can use the device or try to consider alternative options.

- There are no adverse events that could require the device usage to be modified.
- If participants develop cardiac arrhythmias, the device will not be used during that treatment period.
- Device usage will not be modified in accordance with the participants' results.
- The device setting/dose is modified to minimise local ear discomfort [i.e., current reduced on participant request].
- If the first treatment period is interrupted for clinical or device-related reasons, the Principal Investigator will be informed; proceeding with further treatment on the following day will be permitted as long as there are no [new] exclusion criteria met and after consultation with the Chief Investigator.
- The hardware of the device will not need to be modified during the study duration.

The most likely scenario we anticipate is the interruption of a treatment session. It is possible that patient stops the device or removes the electrode clips from the ear(s) before the duration of the session is complete. In that case, we will advise to reattach the device again for the remaining period and record the interruption. If they are not able to use the device for the full stimulation period, we will record a protocol deviation.

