# 7.0 Participant, study, and site discontinuation

It is always within the remit of the responsible clinician to withdraw the participant from the study for appropriate medical reasons. This can be (but is not limited to) individual adverse events, new information gained about a treatment, or if it is felt to be in the participant's best interest. Specific circumstances where participants will be withdrawn from the study are if the auricular stimulation site became inflamed and/or painful.

- If a participant's Personal or Professional consultee wishes to withdraw, data collection and follow-up would continue for withdrawn participants enabling these data to still be used.
- No further blood samples would be collected for withdrawn participants.
- The reasons for participant withdrawal and follow-up information collected would be recorded and timed.
- Participants will not be replaced.
- Withdrawn participants could not be re-entered on this study.
- Clinical data for participants or their representatives that have withdrawn from the study will
  be kept only up until the date they withdrew, unless they also request for their study data to
  be deleted.
- Already collected samples and data would be used [intention-to treat analysis].
- Participants who have become lost to follow-up by seven days will be documented.

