# NIH Stroke Scale (NIHSS) measured before the start of mechanical thrombectomy and 24 hours after the procedure.

NIHSS will be assessed at the following time points by a member of the research team:

- any time point after admission to hospital but before induction of anaesthesia
- 24 hours from start of mechanical thrombectomy

Clinically recorded arrhythmias within the first 24 hours after the start of mechanical thrombectomy Defined as electrocardiograph evidence for cardiac rhythm as determined by the treating clinician either documented in the medical records and/ or recorded by a 12 lead ECG.

Absolute levels of serum high-sensitivity troponin-T levels measured before the start of the first transcutaneous autonomic neuromodulation and at the end of the second transcutaneous autonomic neuromodulation.

Additional blood samples to routine care will be collected to measure serum high sensitivity troponin-T (Elecsys, Roche Diagnostics) levels. Blood samples will be collected at any time after hospital admission but before the induction of anaesthesia and within two hours upon the completion of the second transcutaneous autonomic neuromodulation. The time of completion for transcutaneous autonomic neuromodulation is defined as when the device is switched 'on' and 'off' by a member of the research team. If blood samples are not collected, a protocol deviation will be recorded and data point classified as 'missing'.

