Appendix 1: Derived outcomes and variables

Primary outcome

CV systolic blood pressure:
$$CV = \left(\frac{SD}{BP_{mean}}\right) * 100$$

Secondary outcomes

For both systolic BP (SBP) and diastolic BP (DBP), the following indices of blood pressure variability will be calculated:

1. Standard deviation SBP/DBP in the first 24h after mechanical thrombectomy.

$$SD = \sqrt{\frac{1}{(n-1)}\sum_{(i=1)}^{(n)} (BP_i - BP_{mean})^2}$$

2. Average real variability in the first 24h after mechanical thrombectomy.

$$ARV = \frac{1}{\sum_{k}^{w_k} \sum_{k=2}^{n} w_k \times |BP_k - BP_{k-1}|}$$

3. Successive variation in the first 24h after mechanical thrombectomy.

$$SV = \sqrt{(1/(n-1))\sum_{(i=1)}^{(n-1)} (BP_{i+1} - BP_i)^2)}$$

4. Residual standard deviation in the first 24h after mechanical thrombectomy.

$$rSD = \sqrt{\frac{\sum (BP - BPest)^2}{n - 2}}$$

Heart rate variability, time domain measures

RR-interval, SDNN, RMSSD, SD HR, NN, pNN

Frequency domain measures

VLF power, VLF peak, LF power, LF peak, HF power, HF peak, DFA1, DFA2.

Peak level of Troponin-T measured within 24 hours of MT

This is defined as the highest troponin-t value measured within 24 hours of mtwhich is collected on admission and 24h post MT [if applicable]. If only one troponin-T value is available, then this will be used as the peak. If troponin-T data is missing for both timepoints, then the outcome will be set to missing.

Infection up to 7 days after mechanical thrombectomy

This is defined as one or more of the following infections (definitions of each type of infection are the same used in the SPACE protocol):

- Superficial surgical site infection
- Deep surgical site infection
- Organ space surgical site infection
- Urinary tract infection
- Infection, source uncertain
- Laboratory confirmed blood stream infection

Equal to 1 if:

- At least one of the components of infection is listed as occurring Equal to 0 if:
- All of the components of postoperative infection are "None"

Missing if:

- All components are missing
- OR one or more of the components of postoperative infection is missing and all other components are "None"

Death and location 7 days after mechanical thrombectomy

Equal to 1 if:

• Patient status at 7-day follow-up is dead/in hospital

[figure not shown]
Equal to 0 if:

• Patient status at 7-day follow-up is alive / out of hospital

Missing if:

- Patient status at 30-day follow-up is missing

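### Two unranked rules for a sore ear: section 7.0 withdraws the patient from the study and stops blood sampling, section 10.11 only withholds or reduces stimulation (minor)

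*Protocol*

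**What the plan says.** **Protocol 7.0** makes an ear reaction a named ground for leaving the study: "Specific circumstances where participants will be withdrawn from the study are if the auricular stimulation site became inflamed and/or painful". It sets no severity threshold. It adds: "No further blood samples would be collected for withdrawn participants".

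**Protocol 10.11** treats ear events as a matter of device use. If irritation or dermatitis makes the clips hard to wear, "we will withhold treatment until the person can use the device or try to consider alternative options". For lesser complaints, "The device setting/dose is modified to minimise local ear discomfort", by reducing the current at the participant's request. Withdrawal is not mentioned, and 10.5 has every non-compliant participant followed up.

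**Data after withdrawal.** Two bullets in 7.0 deal with this. Where a consultee wishes to withdraw, "data collection and follow-up would continue for withdrawn participants enabling these data to still be used". For participants or representatives who have withdrawn, clinical data are "kept only up until the date they withdrew". A third bullet says that samples and data already collected are used under intention to treat.

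**Second troponin sample.** Protocol Appendix A times it "within two hours upon the completion of the second transcutaneous autonomic neuromodulation" and classes an uncollected sample as a protocol deviation and missing. The schedule in Protocol 6.2 and the SAP's exploratory objectives place it at 24 h. SAP Appendix 1 adds: "If only one troponin-T value is available, then this will be used as the peak". SAP Table 6 reports the change from admission.

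**The concern.** Protocol 1.3 names local skin irritation as the device's only established risk, so it is the device event that staff are most likely to meet. They have two instructions for it. One ends the patient's participation and blood sampling; the other pauses or turns down the stimulation.

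Under 7.0, a reaction acted on after session 1 or during session 2 removes the second troponin sample. The patient then has no change from admission, and the admission value stands as the peak, which can only equal or understate the true peak. It is also unclear whether blood pressure, NIHSS and day-7 status go on being collected, in a patient whose device reaction the trial particularly needs to follow. Removing a patient from the study because stimulation was not tolerated sits awkwardly with an analysis by randomised group irrespective of compliance (Protocol 14.2).

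**Working it through.** **1. Do the two rules cover the same events?**

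| Event | Protocol 7.0 | Protocol 10.11 |
|---|---|---|
| Ear discomfort | Withdraw, if it amounts to pain | Lower the current |
| Irritation or dermatitis, clips hard to wear | Withdraw, if inflamed or painful | Withhold until usable, or consider alternatives |
| Further blood samples | None | Not restricted |

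Dermatitis is inflammation of the skin, and discomfort shades into pain. The middle row therefore falls under both rules, with different consequences. That 10.11 keeps the patient in the study is an inference: withholding until the device can be used presupposes continued participation, and 10.5 follows up non-compliers.

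**2. What is lost under 7.0?**

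- Withdrawal before the post-session-2 sample: second troponin and change from admission missing.
- Withdrawal after that sample: no troponin loss.
- Systolic readings already taken: used. Appendix A sets no minimum number of readings, so a coefficient of variation can still be calculated, from a shorter record if collection stops.
- Later blood pressure, NIHSS and day-7 status: not stated. One 7.0 bullet is limited to a consultee's wish and the other to participants or representatives who have withdrawn. They point in opposite directions, and neither names the clinician's decision.

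**3. What happens under 10.11 if session 2 is withheld?** Appendix A's two-hour window has no starting point. Protocol 6.2 and the SAP point to 24 h, so this is an inconsistency in timing, and the missing-sample rule applies if nothing is drawn.

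**4. How many patients?** Protocol section 1 (Efficacy/Safety/Tolerability) gives 3 of 86 with minor ear irritation.

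- Rate: 3/86 = 3.5%. Exact (Clopper-Pearson) 95% limits: 0.7% to 9.9%.
- Expected number = n × p; chance of at least one = 1 − (1 − p)^n.
- If the clips are the cause, both arms are exposed (Protocol 6.1 and 6.7 fit them to everyone). With n = 36: 36 × 0.0349 = 1.3 patients (0.3 to 3.5); chance of at least one 72% (23% to 98%).
- If only active stimulation causes it, n = 18: 18 × 0.0349 = 0.6 patients (0.1 to 1.8); chance of at least one 47% (12% to 85%).

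**5. Would primary power suffer?** The plan's sample size is reproduced first. SAP inputs: 15 v 10, SD 4, 5% non-compliance in each group, 90% power, two-sided 5%. Diluted difference = 5 × (1 − 0.05 − 0.05) = 4.5. A two-sample t test needs 17.6, so 18 per arm and 36 in total, as stated.

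Now suppose, as a worst case that the documents do not state, that an affected patient's primary value were lost altogether:

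| Patients analysed | Power |
|---|---|
| 18 v 18 | 90.6% |
| 17 v 18 | 89.8% |
| 16 v 17 | 87.9% |
| 16 v 16 | 86.8% |

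The last row, four lost, exceeds the upper limit of 3.5 patients in step 4.

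**The case against.** The best defence is that the rules form a ladder: discomfort, lower the current; irritation, withhold; inflamed or painful, withdraw. This does not hold. The second rung already includes dermatitis and ears that cannot tolerate the clips, while the third is triggered by any pain. The order is neither stated nor consistent.

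The other objections largely stand, and they limit the point.

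- A reader might infer that no data rule covers a stop made by the clinician. That goes too far. Already collected data are used (7.0), an uncollected sample is missing (Appendix A), randomised patients with a recorded outcome are analysed (SAP, General analysis principles), and a lone troponin value serves as the peak (SAP Appendix 1). The gap is only whether later collection continues.
- A reader might infer that the second troponin is always lost under 7.0. It is lost only if withdrawal comes first.
- A reader might infer that the bullet limiting retention to the withdrawal date cuts off these patients' data. Its wording is about participants or representatives who withdrew, so it does not clearly reach a clinician's decision.
- The understated peak has little reach: no SAP dummy table reports peak troponin.
- A reader might infer bias between arms. Clips are worn in both arms and the current is set below the tingling threshold (Protocol 10.8), so imbalance is possible but not shown.

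**Conclusion.** The conflict between 7.0 and 10.11 is real and should be removed, but it is minor. It concerns about one patient, may cost that patient a second troponin value and the change from admission, and leaves later data collection undefined. Protocol 14.4 reports myocardial injury without testing, and SAP Table 6 has no p-value column. The primary comparison is not materially affected, and the sample size is not in question.

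The size rests on applying 3/86 to this trial. Those irritations were mild and needed no treatment (Protocol 1.3), so the figure is an upper reading of a trigger that requires inflammation or pain. It comes from orthopaedic trauma patients, and whether it carries over to thrombectomy patients, who are anaesthetised or sedated for the first session, is an assumption. The limits of 0.3 to 3.5 patients reflect sampling error only.

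**What to change.** - **Protocol 7.0:** replace study withdrawal for an ear reaction with: *stimulation is stopped; blood sampling, 24 h data and day-7 follow-up continue unless the patient or consultee withdraws*. This also supplies the data rule for a stop made by the clinician.
- **Protocol 10.11:** give one ordered rule: lower the current for discomfort; remove the clips and withhold stimulation if the site is inflamed or painful.
- **Protocol Appendix A:** when session 2 is not given, take the second troponin sample 24 h after the start of thrombectomy and record the actual time.

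This takes a few lines of amendment, with no new visits or patients. There are two downsides. A patient with a sore ear still has the planned second blood draw, and a 24 h sample may fall some hours from the time used for patients sampled after session 2.

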#### 10.12 Management of device-specific adverse events

Any device-specific adverse events (AEs) will be recorded in the patient medical records and eCRF and the information – in pseudo anonymised format – will be passed on to the delegated representative from Afferent Medical Solutions Ltd.

All AEs will be informed to the device manufacturer (Afferent Medical Solution Ltd) as soon as possible after the investigation site staff has become aware of the event. Details of the device-specific adverse will events be sent to the Afferent team on the following email [contact], and where possible, a member of the trial team will contact the Afferent team via phone at [name].

We anticipate following side effects associated with TAN applied via electrical stimulation for the tragus:

- Light-headedness
- Fatigue/tiredness
- Mood changes
- Neck pain
- Tooth pain
- Pain/local skin irritation due to attachment of the device ear clips
- Tingling sensation due to the use of the device
- Palpitations

AEs will be recorded in the medical notes and on the appropriate AE pages of the CRF corresponding to the visit or interaction with the study team. Serious adverse events (SAEs) require expedited reporting to the device manufacturer (Afferent Medical Solution Ltd) and the Sponsor or designee regardless of relationship to study device or study procedure (refer for more information to

Investigators Brochure 9.3). All those will be informed as soon as possible and within 24 hours of the Investigator/ Investigation site staff become aware of the event. Potential interactions with other therapies any Device related SAEs are not anticipated. However, if they occur, the Principal Investigator and Investigation site will follow Afferents SOPs for reporting and managing them. Please see CIP section 13 for further information.

#### 10.13 Potential interactions with other therapies

We do not anticipate any adverse interactions between existing medications and TAN treatment, except it is possible that those on beta-blockers may have an increased blood pressure lowering effect with the use of device. This is because TAN is likely to augment vagal tone, whereas beta-blockers inhibit sympathetic effects, and both of these could be additive for the patient. Similarly, drugs that increase the parasympathetic stimulation, such as clonidine may also increase the blood pressure efficacy of the device. However, clonidine is rarely used nowadays, and certainly not amongst first line medications for the treatment of high blood pressure.

#### 10.14 Management of incorrect usage

The product has been designed for use by only one patient. It must not be re-used by other patients. If the product fails to operate as described by the IFU (Appendix B) or malfunctions in any way a Product Complaint Reports as set out in Appendix G should be filed and submitted directly to Afferent Medical Solutions Ltd ([contact]).

### 10.15 Precautions regarding contraception

Pregnancy is an exclusion criteria.

#### 10.16 Arrangements for post-study access to investigational device

We will follow-up all participants for a period of seven days after the completion of the last stimulation period, no further access is possible

# 11.0 Safety Reporting

# 11.1 Site investigator assessment

The Principal Investigator is responsible for the care of the participant, or in their absence an authorised medic within the research team is responsible for assessment of any event for:

- Seriousness
   Assessing whether the event is serious according to the definitions given in section Error!

   Reference source not found...
- Causality
  Assessing the causality of all serious adverse events in relation to the study treatment according to the definition given. If the SAE is assessed as having a reasonable causal

relationship with the investigational device, then it is defined as an ADE.

Expectedness

Assessing the expectedness of all ADEs according to the definition given. If the ADE is unexpected (as per the risk analysis or other Reference Safety Information (RSI) document), then it is a USADE.

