# II. Glossary of terms and abbreviations

AE Adverse Event

ADE Adverse Device Event
AR Adverse Reaction
BP Blood Pressure

APR Annual Progress Report

DMEC Data Monitoring and Ethics Committee

eCRF Electronic Case Report Form

GCP Good Clinical Practice
ISF Investigator Site File

JRMO Joint Research Management Office

MHRA Medicines and Healthcare products Regulatory Agency

Participant An individual who takes part in a clinical study

QMUL Queen Mary University of London

REC Research Ethics Committee
RSI Reference Safety Information

SAE Serious Adverse Event

SADE Serious Adverse Device Event
SAR Serious Adverse Reaction
SDA Source Data Agreement

SUSAR Suspected Unexpected Serious Adverse Reaction
TAN Transcutaneous autonomic neuromodulation

TMF Trial Master File

TMG Trial Management Group
TSC Trial Steering Committee

USADE Unexpected Serious Device Event
WHRI William Harvey Research Institute

VANS v3.0 20.04.2023 Page 4 of 44

Chief Investigator name: [name]

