#### 6.4 Blinding

This is a triple-blind trial, with trial participants, care providers and endpoint assessors to the treatment group allocation. The primary outcome will be analysed by individuals masked to the patient treatment allocation and clinical outcomes. Afferent Medical Solutions Ltd will be unblinded to facilitate reporting of Serious Adverse Device Events (SADE) or Unexpected Serious Adverse Device Events (USADEs) to the MHRA. The blinded interventions are highly comparable, as the same device will be used for all participants randomized to either active stimulation or turned off. Final unblinding of all study participants will occur after the data set is locked.

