# 11.5 Device Adverse Reporting Failures, Malfunctions and Re-use

All device deficiencies will be recorded on the clinical investigation device deficiency log and where appropriate in the participant's medical records. Device deficiencies which could have caused a SADE must be reported to the device manufacturer (Afferent Medical Solution Ltd) and the Sponsor within 24 hours of becoming aware of the event by submitting a Device Reporting Form to [contact]. Device deficiencies must be recorded and reported throughout the Clinical Investigation. AffeX-CT has been specifically designed to be used by only one patient and must not be re-used by other patients.

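### Protocol section 11.1 assesses causality only for serious events and labels a related serious event an ADE, so it has no causality step for non-serious device effects and no step that yields a SADE

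*Protocol*

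**What the plan says.** Protocol section 11.1 gives the site assessment to the Principal Investigator, or "in their absence an authorised medic within the research team is responsible for assessment of any event for" seriousness, causality, expectedness and severity. The causality bullet is narrower than that lead-in: "Assessing the causality of all serious adverse events in relation to the study treatment according to the definition given". An SAE found to have a reasonable causal "relationship with the investigational device, then it is defined as an ADE". The next bullet builds on that label: "Assessing the expectedness of all ADEs according to the definition given". An ADE that is unexpected against the Reference Safety Information (RSI) becomes a USADE. SADE does not appear in these steps.

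Other sections do use SADE. The glossary has its own line, "SADE Serious Adverse Device Event", apart from ADE and USADE. Section 6.4 states that "Afferent Medical Solutions Ltd will be unblinded to facilitate reporting of Serious Adverse Device Events (SADE", and goes on to name USADEs as well and the MHRA as the recipient. Section 11.5 makes SADE a reporting trigger: "Device deficiencies which could have caused a SADE must be reported to the device manufacturer" and to the sponsor, within 24 hours.

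On the harms themselves, section 1.3 names local skin irritation of the outer ear as the only established risk. Section 10.12 lists eight anticipated effects of stimulation, among them "Pain/local skin irritation due to attachment of the device ear clips".

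**The concern.** A device trial normally sorts events by two independent questions: is the event serious, and is it related to the device? Section 11.1 asks the second question only when the answer to the first is yes, and then gives the related serious event the name that belongs to any related event, serious or not. Two things follow.

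- The effects that the protocol itself expects, which are mostly of a kind that would be non-serious, get no investigator assessment of relatedness under 11.1.
- A serious, related but expected event is called an ADE, while 6.4 and 11.5 rely on the SADE label for regulatory and deficiency reporting.

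At stake is how clearly the device's harms can be described at the end of a pilot meant to inform a larger trial, and whether site staff and the manufacturer mean the same thing by the same term.

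**Working it through.** No formula applies. The check is to take each kind of event through the steps of 11.1 as written and compare the result with the terms used elsewhere.

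| Event | Causality step in 11.1? | Label from 11.1 | Label implied by the glossary terms |
|---|---|---|---|
| Non-serious, caused by the device | No | None | ADE |
| Serious, unrelated | Yes | SAE | SAE |
| Serious, related, expected | Yes | ADE | SADE |
| Serious, related, unexpected | Yes | USADE | USADE |

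None of the four routes ends in SADE. One ends in USADE, as it should. One has no causality step at all, and one carries a label that fits a wider class. Within 11.1, ADE has taken on the content of SADE.

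The other sections show whether this is repaired elsewhere.

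- **11.3** groups ADEs with ordinary AEs, which makes sense only if an ADE can be non-serious; under 11.1 it cannot. The same section first sends all AEs and ADEs to the notes and the CRF, and then says that a non-serious event is not entered as an AE on the CRF.
- **11.7** includes relatedness in the Chief Investigator's review of SAEs and reportable device deficiencies. For non-serious AEs the Chief Investigator is to confirm agreement periodically, but 11.1 supplies no site causality call to agree with.
- **10.12** has device-specific events recorded in the notes and eCRF and passed to the manufacturer, with no condition on seriousness. It does not say who decides that an event is device-specific, or by what criterion. Its list attributes two of the eight effects to the device in so many words (clip irritation and tingling). The other six, such as light-headedness, fatigue and palpitations, could equally arise from a stroke or from a procedure under anaesthesia or sedation.
- **14.5** has ear irritation, pain and dermatitis recorded.
- **SAP, Safety analyses and Table 7** count AEs and SAEs by arm, with rows for cardiac arrhythmia, local skin irritation and other. There is no device-related, ADE or SADE category.

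So other sections capture the events, but none supplies the missing causality step or the missing label.

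The protocol gives one figure that suggests scale: 3 of 86 participants in the group's recent study had minor ear irritation. If that proportion carried over, 36 × 3/86 ≈ 1.3 participants would be expected here. This is only an illustration, because the population and the length of stimulation differ.

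**The case against.** The strongest reply is that nothing is lost in practice. Section 10.12 treats device-specific AEs as a category of its own. It also requires SAEs to reach the manufacturer and the sponsor within 24 hours regardless of relationship, and says that device-related SAEs are not anticipated. Section 11.6 reports SAEs to both as well, although it has exemptions and a narrower sentence confined to related and unexpected events. Unexpected related SAEs still become USADEs, and the unblinded manufacturer reports to the MHRA. SAP Table 7 shows skin irritation and arrhythmia by arm, and in a randomised sham-controlled trial the comparison of arms says something about attribution without any individual causality call. Finally, 11.1 refers to definitions given elsewhere, and the Investigator Brochure, which is not among the documents reviewed, may contain them.

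Most of this stands, and it rules out two stronger readings that a reader might infer. The first is that expected device effects are never treated as device-related. That is true of 11.1 alone; 10.12, 14.5 and Table 7 deal with them. The second is that serious related events escape reporting, or that a SADE count is forced to zero. The documents plan no SADE count, and a missing label is not a missing report.

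Two parts of the reply do not stand. A conventional definition in the brochure would not cure the problem, because 11.1 states its own rule for what an ADE is and the two would then conflict. And the comparison of arms cannot isolate harm from the ear clips: under 6.7 every participant, active or sham, has the device connected to both ears. Irritation from the clips can occur in both arms, and only an event-level assessment can record it as device-related.

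**Conclusion.** The point holds as an error of classification in 11.1. Causality is not assessed for non-serious events, which include the only established device risk, and no step produces the SADE class that the glossary, 6.4 and 11.5 use. Of the four kinds of event traced, one goes unassessed and one is mislabelled.

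The practical size is modest. Events are still recorded and reported through other sections. The mislabelled class (serious, related and expected) should be rare on the protocol's own expectation, and the primary endpoint is unaffected. What is missing is a recorded, criterion-based relatedness call for the harms most likely to occur.

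This rests on two assumptions: that 11.1 is applied as written, and that most of the effects listed in 10.12 would be non-serious. The second is a matter of ordinary expectation, not a figure in the documents. The documents do not support the conclusion that the trial would be unable to report its expected harms at all.

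**What to change.** Rewrite 11.1 so that causality is assessed for every AE, with three definitions in sequence: a related AE is an ADE, a related SAE is a SADE, and a SADE not covered by the RSI is a USADE. State who makes the call for non-serious events and by what criterion, and keep that person blinded to allocation.

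Then reconcile 11.1 with 6.4, 10.12 and 11.5 so that each term means the same throughout, and check it against the Investigator Brochure. Section 11.3 must be settled in the same amendment. While its sentence keeping non-serious events from being entered as AEs on the CRF stands, a causality field on the AE page would stay empty for exactly the events in question.

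In the SAP, report device-related events by arm in Table 7.

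The cost is a wording amendment, one CRF field and one table column. No change to treatment, sample size or the primary analysis is involved.
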